4.4. Sponsor's Qualified Medical Personnel

The contact information for the sponsor's appropriately qualified medical personnel for the study is documented in the study contact list located in the supporting study documentation.

To facilitate access to appropriately qualified medical personnel on study-related medical questions or problems, patients are provided with a contact card. The contact card contains, at a minimum, protocol and investigational product identifiers, patient study numbers, contact information for the investigator site, and contact details for a contact center in the event that the investigator site staff cannot be reached to provide advice on a medical question or problem originating from another healthcare professional not involved in the patient's participation in the study. The contact number can also be used by investigator staff if they are seeking advice on medical questions or problems; however, it should be used only in the event that the established communication pathways between the investigator site and the study team are not available. It is therefore intended to augment, but not replace, the

PF-06863135

C1071001

Final Protocol Amendment 9, 28 March 2023

established communication pathways between the investigator site and the study team for advice on medical questions or problems that may arise during the study. The contact number is not intended for use by the patient directly, and if a patient calls that number, he or she will be directed back to the investigator site.

5. STUDY TREATMENTS

For the purposes of this study, and per International Conference on Harmonization (ICH) guidelines, investigational product is defined as a pharmaceutical form of an active ingredient or placebo being tested or used as a reference/comparator in a clinical trial, including a product with a marketing authorization when used or assembled (formulated or packaged) in a way different from the approved form, or when used for an unapproved indication, or when used to gain further information about an approved use (ICH E6 1.33).

For this study, the investigational medicinal products include PF-06863135, lenalidomide, pomalidomide and dexamethasone. For dose level information, please see [Section 3.1](#).

5.1. Allocation to Treatment

Dose level allocation will be performed by the sponsor after patients have given their written informed consent and have completed the necessary baseline assessments. The site staff will e-mail a complete Registration Form to the designated sponsor study team member or designee. The sponsor will assign a patient identification number and supply this number to the site. The patient identification number will be used on all study-related documentation at the site.

No patient shall receive investigational product until the investigator or designee has received the following information in writing from the sponsor:

- Confirmation of the patient's enrollment;
- Specification of the dose level for that patient and;
- Permission to proceed with dosing the patient.

The sponsor or designee will notify the other sites of the inclusion of a new patient, and will inform study sites about the next possible enrollment date.

5.2. Patient Compliance

All doses of PF-06863135 will be administered by the appropriately designated study staff at the investigational site. Oral medications lenalidomide, pomalidomide, and dexamethasone, if applicable, will be taken by the patient either at the site or at home.

The site will complete required dosage Preparation Record located in the Investigational Product manual (IP manual). The use of the Preparation Record is preferred but it does not preclude the use of an existing appropriate clinical site documentation system. The existing clinical site's documentation system should capture all pertinent/required information on the

PF-06863135

C1071001

Final Protocol Amendment 9, 28 March 2023

preparation and administration of the dose. This may be used in place of the Preparation Record after approval from the sponsor and/or designee.

5.3. Investigational Product Supplies

5.3.1. Pharmaceutical Form(s) and Packaging

PF-06863135 is presented as a sterile aqueous buffered solution for intravenous/subcutaneous administration. Please consult the Investigational Product Manual (IP manual) and Investigator's Brochure for further details.

Lenalidomide (Revlimid®) is an oral medication approved in the US, EU, and Canada for the treatment of multiple myeloma. Please consult the Revlimid® US package Insert (USPI) or EU Package Insert or SPC for further details.³⁰⁻³²

Pomalidomide (US Pomalyst®, EU and Canada Immovid®) is an oral medication approved in the US, EU, and Canada for the treatment of multiple myeloma. Please consult the Pomalyst® US package Insert (USPI) or EU package insert or SPC for further details.³⁴⁻³⁶

Dexamethasone is an oral medication approved in the US, EU, and Canada.³⁷

5.3.2. Preparation and Dispensing

For PF-06863135, see the IP manual for instructions on how to prepare the investigational product for administration. Investigational product should be prepared and dispensed by an appropriately qualified and experienced member of the study staff (eg, physician, nurse, physician's assistant, nurse practitioner, pharmacy assistant/technician, or pharmacist) as allowed by local, state, and institutional guidance.

Only qualified personnel who are familiar with procedures that minimize undue exposure to themselves and to the environment should undertake the preparation, handling, and safe disposal of biotherapy agents.

5.4. Administration

5.4.1. IV Administration PF-06863135

PF-06863135 will be administered on Day 1, 8 and 15 of each cycle per the IP manual as an intravenous (IV) infusion over 2 hrs (± 15 minutes). If the patient is assigned to the lead-in cohort in Part 2 that is specifically designed to evaluate reduced infusion time, PF-06863135 may be administered as an IV infusion over 1 hr (± 10 minutes). For monotherapy, each cycle will be 3 weeks in duration, and each patient will be treated 3 times during each cycle, unless dose delays or interruptions occur (see [Sections 5.5.1](#) and [5.5.2](#)). On C1D1 for all patients, and on C0D1 for patients receiving a priming dose, PF-06863135 will be administered on an inpatient basis. On all other days, PF-06863135 will be administered on an outpatient basis.). On C1D1 for all patients, and on C0D1 for patients receiving a priming dose, PF-06863135 will be administered on an inpatient basis. On all other days, PF-06863135 will be administered on an outpatient basis.

PF-06863135

C1071001

Final Protocol Amendment 9, 28 March 2023

Details for PF-06863135 infusion are provided in the current PF-06863135 IP Manual. The dose level will be assigned by the sponsor (see [Section 5.1 Allocation to Treatment](#)). For monotherapy Part 1, all patients should be weighed within 72 hours prior to Day 1 of each cycle to ensure they did not experience either a weight loss or gain >10% from the prior weight used to calculate the amount of PF-06863135 required for dose preparation. If the patient experienced either a weight loss or gain >10% compared to the prior weight used to calculate the initial dose or dose in the previous cycle, the amount of PF-06863135 required for preparation and administration for the current cycle must be recalculated using this most recent weight obtained. Should the institutional policy be such that the dose is required to be calculated if a patient experiences a weight gain of <10%, this will be allowed. Fixed dosing approach will be applied in dose-finding for combination and also-dosing approach will be applied in dose-finding for combination and also in all expansion parts of the study (See [Section 1.2.9.4](#)).

The use of an infusion or syringe pump is the preferred method of administration to ensure accurate delivery of the investigational product. Please refer to the IP manual for infusion rate and duration.

Each patient may receive PF-06863135 until disease progression, unacceptable toxicity, withdrawal of consent, or study termination. If a patient has received treatment with Q1W PF-06863135 for at least 6 months, and disease assessments have remained stable over at least 2 months, consideration may be given to increasing dose intervals from weekly to every 2 weeks or once per cycle (only CXD1 dosing and activities applicable) after consultation with sponsor. Cycles would remain the same length with any skipped weekly doses noted. If the patient subsequently begins to have increase of disease burden, dose intervals should return to weekly dosing.

5.4.2. SC Administration PF-06863135

Qualified and trained investigator site personnel will administer PF-06863135 to patients by SC injection. Ideally, each injection may be up to 2 mL in volume. However, if the maximum volume allowed per institution's policy is lower, the number of injections may increase to accommodate this difference in volume to ensure the correct final dose is delivered.

Study drug should be administered to the abdomen (with preference given to the lower quadrants when possible). Refer to [Appendix 9](#) for details on administration of multiple injections to the abdomen. Study staff should refer to the IP Manual for specific instructions on the handling and preparation of study drug.

Similar to IV dosing, during monotherapy dose escalation with Q1W SC PF-06863135 only each cycle will be 3 weeks in duration, and each patient will be treated 3 times during each cycle, unless dose delays or interruptions occur (see [Sections 5.5.1](#) and [5.5.2](#)). If patients are enrolled into Q2W SC dosing cohorts during dose escalation, each cycle will be 4 weeks in duration, and each patient will be treated twice during each cycle. On C1D1 for all patients, and on C0D1 for patients receiving a priming dose, PF-06863135 will be administered on an inpatient basis. On all other days, PF-06863135 will be administered on an outpatient basis).

PF-06863135

C1071001

Final Protocol Amendment 9, 28 March 2023

If patients are enrolled into Q2W SC dosing cohorts during dose escalation, each cycle will be 4 weeks in duration, and each patient will be treated twice during each cycle. On C1D1 for all patients, and on C0D1 for patients receiving a priming dose, PF06863135 will be administered on an inpatient basis. On all other days, PF06863135 will be administered on an outpatient basis.

Details for PF-06863135 injections are provided in the current PF-06863135 IP Manual. The dose level will be assigned by the sponsor (see [Section 5.1 Allocation to Treatment](#)). For monotherapy Part 1, all patients should be weighed within 72 hours prior to Day 1 of each cycle to ensure they did not experience either a weight loss or gain >10% from the prior weight used to calculate the amount of PF-06863135 required for dose preparation. If the patient experienced either a weight loss or gain >10% compared to the prior weight used to calculate the initial dose or dose in the previous cycle, the amount of PF-06863135 required for preparation and administration for the current cycle must be recalculated using this most recent weight obtained. Should the institutional policy be such that the dose is required to be calculated if a patient experiences a weight gain of <10%, this will be allowed. Fixed-dosing approach will be applied in dose-finding for combination and also in all expansion parts of the study (See [Section 1.2.9.4](#)).

Each patient may receive PF-06863135 until disease progression, unacceptable toxicity, withdrawal of consent, patient no longer willing to participate in trial, or study termination. If a patient has received treatment with Q1W PF-06863135 for at least 6 months, and disease assessments have remained stable over at least 2 months, consideration may be given to increasing dose intervals from weekly to every 2 weeks or once per cycle (only CXD1 dosing and activities applicable) after consultation with sponsor. Cycles would remain the same length with any skipped weekly doses noted. If the patient subsequently begins to have increase of disease burden, dose intervals should return to weekly dosing.

For Parts 1C, 1D, 1E and Part 2 dose expansion: PF-06863135 will be administered as described for monotherapy PF-06863135, and each cycle will be 4 weeks in duration. On C1D1 for all patients and C0D1 for patients receiving a priming dose, PF-06863135 will be administered on an inpatient basis. On all other days, PF-06863135 will be administered on an outpatient basis.

If a patient has received treatment with Q1W PF-06863135 for at least 6 months, and disease assessments have remained stable over at least 2 months, consideration may be given to increasing dose intervals from weekly to every 2 weeks or once per cycle (only CXD1 dosing and activities applicable) after consultation with sponsor. Cycles would remain the same length with any skipped weekly doses noted. For every 2 week dosing, it would be preferable to skip dosing of PF-06863135 on days 8 and 22 of each cycle. If the patient subsequently begins to have increase of disease burden, dose intervals should return to weekly dosing.

5.5. Recommended Dose Modifications

Every effort should be made to administer investigational product on the planned dose and schedule.

PF-06863135

C1071001

Final Protocol Amendment 9, 28 March 2023

In the event of significant toxicity, dosing may be delayed and/or reduced as described below. In the event of multiple toxicities, dose modification should be based on the worst toxicity observed. Patients are to be instructed to notify investigators at the first occurrence of any adverse symptom.

Dose modifications of PF-06863135, lenalidomide, pomalidomide and dexamethasone, may occur in one of three ways:

- Within a cycle: dosing interruption until adequate recovery and dose reduction, if required, during a given treatment cycle;
- Between cycles: next cycle administration may be delayed due to persisting toxicity when a new cycle is due to start;
- In the next cycle: dose reduction may be required in a subsequent cycle based on toxicity experienced in the previous cycle.

In Parts 1E and 2E, if a dose of PF-06863135 is delayed or interrupted, then dexamethasone should not be administered until PF-06863135 administration is restarted.

5.5.1. Dosing Interruptions

Patients experiencing Grade 3 or 4 potentially treatment-related toxicity or intolerable drug-related Grade 2 toxicity despite supportive care should have their treatment interrupted.

Appropriate follow-up assessments should be done until adequate recovery occurs as assessed by the investigator. Criteria required before treatment can resume are described in the Dose Delays Section 5.5.2.

Doses may be held as needed until toxicity resolution. Depending on when the adverse event resolved, a treatment interruption may lead to the patient missing all subsequent planned doses within that same cycle or even to delay the initiation of the subsequent cycle.

If the adverse event that led to the treatment interruption recovers within the same cycle, then re-dosing in that cycle is allowed. Doses omitted for toxicity are not replaced within the same cycle. The need for a dose reduction at the time of treatment resumption should be based on the criteria defined in the Dose Reductions Section 5.5.3, unless expressly agreed otherwise following discussion between the investigator and the sponsor.

In the event of a treatment interruption for reasons other than treatment-related toxicity (eg, elective surgery) lasting >3 weeks, treatment resumption will be decided in consultation with the sponsor.

PF-06863135
C1071001
Final Protocol Amendment 9, 28 March 2023

5.5.2. Dose Delays

Re-treatment following treatment interruption for treatment-related toxicity or at the start of any new cycle should not occur until all of the following parameters have been met:

- ANC $\geq 1,000/\text{mm}^3$ for PF-06863135, dexamethasone, and lenalidomide; $\geq 500/\text{mm}^3$ for pomalidomide;
- Platelets count $\geq 25,000/\text{mm}^3$ for PF-06863135 and dexamethasone; $\geq 30,000/\text{mm}^3$ for lenalidomide; $\geq 50,000/\text{mm}^3$ for pomalidomide;
- Non-hematologic toxicities have returned to baseline or Grade ≤ 1 severity (or, at the investigator's discretion, Grade ≤ 2 if not considered a safety risk for the patient).
- Recovery of treatment-emergent peripheral neuropathy to Grade ≤ 1 severity.

If a treatment delay results from worsening of hematologic or biochemical parameters, the frequency of relevant blood tests should be increased as clinically indicated.

If these conditions are met within 3 weeks of treatment interruption or cycle delay, study treatment may be resumed. Refer to the Dose Reductions Section 5.5.3 for adverse events requiring dose reduction at the time of treatment resumption.

If these conditions are not met, treatment resumption must be delayed up to a maximum of 3 weeks. If patients require discontinuation of study treatment for more than 42 days of Day 1 of the current cycle, then study treatment should be permanently discontinued, unless the investigator's benefit/risk assessment suggests otherwise after discussion with the Sponsor's medical monitor.

If a treatment interruption continues beyond the last day of the current cycle, then the day when treatment is restarted will be counted as Day 1 of the next cycle.

Recommended guidelines for dose delays of PF-06863135 for participants who have active [confirmed (positive by regulatory authority-approved test) or presumed (test pending/clinical suspicion)] SARS-CoV2 infection can be found in [Appendix 10](#).

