5.5.3. Dose Reductions

Following dosing interruption or cycle delay due to toxicity, the PF-06863135 dose may need to be reduced when treatment is resumed.

No specific dose adjustments for PF-06863135 are recommended for Grade 1/2 treatment-related toxicity. However, investigators should always manage their patients according to their medical judgment based on the particular clinical circumstances.

Patients experiencing recurrent and intolerable Grade 2 toxicity may resume dosing at the next lower dose level of PF-06863135 once recovery to Grade ≤ 1 or baseline is achieved.

PF-06863135

C1071001

Final Protocol Amendment 9, 28 March 2023

Dose reduction of PF-06863135 by 1 and, if needed, 2 dose levels will be allowed depending on the type and severity of toxicity encountered. Patients enrolled in the first (0.1 µg/kg) cohort will be allowed 1 dose reduction if required. Patients requiring more than 2 dose reductions (or 1 dose reduction for the first cohort) will be discontinued from the treatment and entered into the follow-up phase, unless otherwise agreed between the investigator and the sponsor. If dose reduction of PF-06863135 is needed for any patient who receives fixed doses of PF-06863135 (Parts 1C, 1D, 1E, 2A, 2C, 2D, 2E), the next dose level of PF-06863135 will be 25% lower than the current dose level (eg, from 32 mg to 24 mg, or from 24 mg to 16 mg). All dose modifications/adjustments must be clearly documented in the patient's source notes and case report form (CRF).

Once a dose has been reduced for a given patient, all subsequent cycles should be administered at that dose level, unless further dose reduction is required. Intrapatient dose re-escalation is not allowed.

Patients experiencing a DLT may resume dosing at the next lower dose level (if applicable) once adequate recovery is achieved. Patients experiencing a DLT of prolonged myelosuppression (>42 days) may not resume treatment even if adequate recovery is achieved. No dose reductions are planned for patients experiencing toxicities other than those listed as DLTs. However, patients experiencing recurrent and intolerable Grade 2 toxicity may resume dosing at the next lower dose level once recovery to Grade ≤1 or baseline is achieved. Patients whose hematologic indices improve prior to meeting the criteria for prolonged myelosuppression >42 days may resume dosing at the next lower dose level or permanently discontinue from treatment at the discretion of the investigator.

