Recommended dose reductions for PF-06863135 are described in Table 5.

Table 5. Dose Modifications for PF-06863135 Product-Related Toxicity and for Peripheral Sensory or Motor Neuropathy***

| Toxicity | Grade 1 | Grade 2 | Grade 3 | Grade 4 |
|--|----------------------------------|----------------------------------|--|--|
| Non-hematologic (excluding peripheral neuropathy-see below) | Continue at the same dose level. | Continue at the same dose level. | Withhold dose until toxicity is Grade ≤1, or has returned to baseline, then reduce the dose by 1 level.* | Permanently discontinue.* |
| Hematologic except for lymphopenia, which is expected as part of PF-06863135 mechanism of action | Continue at the same dose level. | Continue at the same dose level. | Withhold dose until toxicity is Grade ≤2, or has returned to baseline, then resume treatment at the same dose level.** If toxicity reoccurs, dosing may be reduced by 1 dose level. If | Withhold dose until toxicity is Grade ≤2, or has returned to baseline, then reduce the dose by 1 level and resume treatment.** If toxicity reoccurs despite dose reduction, dosing may be reduced by |

PF-06863135
C1071001
Final Protocol Amendment 9, 28 March 2023

Table 5. Dose Modifications for PF-06863135 Product-Related Toxicity and for Peripheral Sensory or Motor Neuropathy***

| Toxicity | Grade 1 | Grade 2 | Grade 3 | Grade 4 |
|--|--|---|--|--|
| | | | 
toxicity reoccurs after a maximum of 2 dose level reductions (1 for patients in first cohort), patient may be permanently discontinued from treatment.
 
For platelets, withhold dose if toxicity $\leq 25,000 \text{ mm}^3$ and re-start when platelets have returned to $\geq 25,000 \text{ mm}^3$ or baseline
 | 1 more dose level. If toxicity reoccurs, patient may be permanently discontinued from treatment. |
| Peripheral sensory or motor neuropathy (all causality) See Section 8.4.4 for recommended work-up. | 
Continue at the same dose level.
 
Continue to monitor the participant for signs of worsening neuropathy
 | 
Withhold dose until resolution to Grade ≤ 1, then resume at a reduced dose level.
 
Continue to monitor the participants for signs of worsening neuropathy.
 
If Grade ≥ 2 neuropathy reoccurs, permanently discontinue elranatamab.
 | Permanently discontinue elranatamab. | Permanently discontinue elranatamab |

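### When a Grade 3 non-hematologic toxicity has improved only to Grade 2, Protocol 5.5.2 and Table 5 give opposite answers on restarting PF-06863135, and no text says which governs.

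*Protocol*

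**What the plan says.** Three parts of Protocol Section 5.5 bear on the restart.

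- **5.5.1 Dosing Interruptions** says who is interrupted: "Patients experiencing Grade 3 or 4 potentially treatment-related toxicity or intolerable drug-related Grade 2 toxicity despite supportive care should have their treatment interrupted". It then names one place for the restart conditions: "Criteria required before treatment can resume are described in the Dose Delays Section 5.5.2". It sends the reader to 5.5.3 only to decide whether the dose must be reduced.
- **5.5.2 Dose Delays** introduces its list with the clause "Re-treatment following treatment interruption for treatment-related toxicity or at the start of any new cycle should not occur until all of the following parameters have"; in other words, every item has to be satisfied first. The non-hematologic item begins "Non-hematologic toxicities have returned to baseline or Grade" 1 or below, and adds that the investigator may accept Grade 2 or below "if not considered a safety risk for the patient". After the list it says: "If these conditions are met within 3 weeks of treatment interruption or cycle delay, study treatment may be resumed". Peripheral neuropathy has a separate item, at Grade 1 or below with no discretion.
- **5.5.3 Dose Reductions, Table 5**, non-hematologic row, Grade 3 column, withholds the dose until the toxicity is Grade 1 or below, "or has returned to baseline, then reduce the dose by 1 level". The cell has no Grade 2 option. Its footnote only limits which nausea, vomiting and diarrhea events count.

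**The concern.** A restart rule should give one answer for a given patient on a given day. Here 5.5.1 appoints 5.5.2 as the source of the restart conditions, yet Table 5 carries a recovery threshold of its own that is stricter at one point. Two sites could treat the same situation differently, each with a passage to cite.

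What turns on it is the length of the interruption, and through that whether the 3-week and 42-day limits in 5.5.2 come into play. The choice also feeds the summaries of cycle delays, interruptions and dose reductions (SAP 8.2.3.5) and relative dose intensity (SAP 6.2.1). Enrollment is complete, but Protocol 3.1 allows treatment until about 30 months after the last patient's first treatment, and the summary of changes for Amendment 9 refers to active patients. The rule can therefore still be applied.

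**Working it through.** There is no figure to reproduce. The check sets the two rules side by side and applies them to each situation that can arise after a treatment-related Grade 3 non-hematologic event other than peripheral neuropathy.

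| Situation | 5.5.2 | Table 5, Grade 3 cell | Same answer? |
|---|---|---|---|
| Still Grade 3, above baseline | hold | hold | yes |
| Now Grade 2, baseline Grade 0-1, other parameters met, investigator sees no safety risk | may resume | withhold | **no** |
| Now Grade 2, baseline Grade 0-1, investigator sees a safety risk or another parameter is not met | hold | withhold | yes |
| Now Grade 2, which is the patient's baseline, other parameters met | may resume | may resume, one level lower | yes on timing |
| Now Grade 1 or below, other parameters met | may resume | may resume, one level lower | yes on timing |

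Only the second line conflicts. Three kinds of event lie outside the table:

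- **Peripheral neuropathy** has its own item in 5.5.2 and its own row in Table 5.
- **Grade 4 non-hematologic events** lead to permanent discontinuation under Table 5, which is a separate matter.
- **Nausea, vomiting and diarrhea** call for modification under Table 5 only if they persist at Grade 3 or 4 despite maximal medical therapy.

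The next question is whether any text settles the second line.

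1. **Scope.** 5.5.2 covers every interruption for treatment-related toxicity. It makes no exception for Grade 3.
2. **Cross-references.** 5.5.1 gives restart conditions to 5.5.2 and the need for dose reduction to 5.5.3. 5.5.2 also points to 5.5.3 only for events that need a reduced dose on resumption. Read literally, 5.5.2 decides when to restart and 5.5.3 decides the dose, but the Table 5 cell also decides when.
3. **Strength of wording.** 5.5.2 is phrased with should and may. Table 5 is introduced as a recommendation. Neither outranks the other.
4. **Precedence.** No sentence says which passage prevails when the recovery grades differ.

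**The case against.** The strongest reply is that 5.5.2 is a general floor and Table 5 a stricter specific rule. The 5.5.2 list says when re-treatment should not happen. It serves four drugs and the start of every new cycle, and a site that follows Table 5 also satisfies it. The Grade 2 discretion has work to do elsewhere: Table 5 continues dosing through Grade 2 non-hematologic events, so a new cycle may begin with one, and the pomalidomide text in 5.5.3 allows a restart at Grade 2 or below at the physician's discretion. A Grade 3 event also requires a dose reduction, so the pointer in 5.5.2 leads to the very cell that holds the stricter threshold.

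That reading is possible, but a site has to infer it. 5.5.1 places the restart conditions in 5.5.2, and 5.5.2 gives permission in its own terms: "If these conditions are met within 3 weeks of treatment interruption or cycle delay, study treatment may be resumed". What stands is the warning about the remedy: a single threshold imposed on all non-hematologic toxicity could disturb the new-cycle and pomalidomide uses of 5.5.2.

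A reader might infer more than the documents support:

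- **That Table 5 forces discontinuation of a patient who stays at Grade 2.** The Table 5 cell has no time limit. The 42-day limit is in 5.5.2 and allows an exception on the investigator's benefit/risk assessment after discussion with the medical monitor.
- **That restarting at Grade 2 is, or is not, a protocol deviation.** No passage says. Section 5.5 is headed as recommendations, and SAP 5.2 leaves deviations to be defined before database lock.
- **That the 5.5.3 text on recurrent Grade 2 toxicity is a further instance of this conflict.** It reads "Patients experiencing recurrent and intolerable Grade 2 toxicity may resume dosing at the next lower dose level of PF-06863135 once recovery" to Grade 1 or below or baseline. It concerns recurrent, intolerable Grade 2 events, not recovery from Grade 3. It is worth a consistency check, no more.

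**Conclusion.** The contradiction is real and narrow. For a treatment-related Grade 3 non-hematologic toxicity within the limits above, 5.5.2 and Table 5 give opposite answers on PF-06863135 while the toxicity is at Grade 2, above the patient's baseline, with the other 5.5.2 parameters met and no safety risk seen by the investigator. It does not reach every Grade 3 non-hematologic event that settles at Grade 2.

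Its effect is on the length of interruptions, on whether the 3-week and 42-day limits are reached, and on the exposure summaries that follow. No sample size, error rate or response definition depends on it.

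The number of patients exposed is unknown, because the documents do not say how many remain on treatment. The date of the last patient's first dose is not given either. If it fell no later than about June 2021, when Amendment 8 recorded enrollment as complete, then 30 months on is about December 2023, roughly nine months after Amendment 9 of 28 March 2023. That limits the practical reach. Even so, this is a conflict between two stated dosing rules, not a missing detail, and it should be resolved.

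**What to change.** The sponsor should reconcile Protocol 5.5.2 with the Grade 3 non-hematologic cell of Table 5 for PF-06863135, in one of two ways:

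- align the recovery condition in the two places, including whether the investigator's discretion applies; or
- add a sentence stating which passage governs when they differ.

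The 5.5.3 text on recurrent, intolerable Grade 2 toxicity should then be read against the result. The uses of 5.5.2 for starting a new cycle and for the combination drugs should stay unchanged unless the sponsor means to change them. Which threshold is clinically right is for the sponsor to decide.

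The cost is protocol wording only. No analysis, sample size or data collection changes.
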